5.0 EXPERIMENTAL PROTOCOL

Protocol Design:

This is a single institution, randomized, placebo-controlled clinical study. There will be 3 cohorts: control group, pre-isolation nitrite infusion, and a post-isolation (reinfusion) cohort.

After induction of general anesthesia with propofol (1-1.5 mg/Kg), tracheal intubation, the establishment of central venous access, invasive monitors and maintenance anesthesia with sevoflurane (1-1.5 minimum alveolar concentration) in 50:50 oxygen: air, infusions will be administered based on the randomization assignment.

I. Control Group A placebo (saline infusion) will be administered during the pre-isolation phase and during the reinfusion phase.

II. Pre-Isolation Infusion Group

[figure not shown]

Figure 1: Pre-isolation group schematic: Sodium nitrite will be initiated (pre-isolation infusion group) during the pre-isolation phase. Saline will be administered during the reperfusion period.

III. Post-Isolation (Reinfusion) Group

[figure not shown]

Figure 2: Reinfusion group schematic: Saline will be administered during the pre-isolation period. Sodium nitrite infusion will be initiated just prior to the reinfusion.

For all 3 groups:

Intraoperative arterial and venous blood samples (BS) will be drawn immediately prior to initiation of the infusion (BS1), 5 min prior to infusion of Islet Cells (BS2), 20 min after infusion of Islet Cells (BS3), and 40 min after infusion of Islet Cells (BS4).

Postoperative blood samples will be obtained 24, 48, 72 and 96 hours after the completion of surgery.

Results of routine lab work performed at the routine 3 month follow-up visit will be collected.

Procedure for Sample collection (email from [name] 6/28/16) – to be performed by lab tech in BMR

- 1) *Transferring blood to Eppendorf tubes,*
- 2) *Centrifuging (using a table top min-fuge which we can provide),*
- 3) *Transferring plasma to 4 other vials (1 containing a pre-made solution, which we can provide) and flash freezing all vials in liquid N₂*
- 4) *Taking some of the red cell pellet and adding to vials (containing pre-made solution that we can provide) and flash freezing all vials in liquid N₂*
- 5) *All samples need to be stored at -80C.*

Primary Endpoints:

- Markers of pancreatic function:
 - Blood glucose levels
 - HbA1c levels pre-operatively and at the 3 month post-operative visit
 - Exogenous insulin use
 - Measured from blood samples 24, 48, 72, 96 hours post op & at 3 months post op
- Decrease in reperfusion injury
- Incidence of diabetes post-operatively

Intraoperative blood samples will be analyzed for serum and methemoglobin levels and biochemical markers of oxidative and nitrosative stress, including plasma and hepatic 3-nitrotyrosine, oxidized lipids (isoprostanes, 8-epi-PGF₂α), protein carbonyls and the NO-metabolites, nitrite, nitrate, S-nitrosothiols, C-N-nitroso compounds and heme nitrosyls. If the above processing is not part of the costs, and assuming 30 patients, each with 6 blood draws then running assays for plasma and red cell NOx, C-peptide levels, circulating pro-inflammatory chemokines/cytokines and perform immunophenotyping of monocytes and neutrophils by flow cytometry and mRNA accumulation.

	Sample Name	Blood Glucose	HbA1c	Insulin level exogenous	RF	C-peptide	Circ pro-inflammatory chemokine / cytokines	Immunophenotyping monocytes and neutrophils	mRNA				
Intraoperative													
Prior to infusion	BS1	X	X			X	X	X	X				
5 min prior to Islet cell infusion	BS2	X											
20 mins after infusion of Islet cells	BS3	X											
40 mins after infusion of Islet cells	BS4	X											
Post-op													
24 hours	BS5	X		X		X	X	X	X				
48 hours	BS6	X		X		X	X	X	X				
72 hours	BS7	X		X		X	X	X	X				
96 hours	BS8	X		X		X	X	X	X				
Follow up													
Clinic visit 3 months post-op	BS9	X	X	X		X	X	X	X				

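### Exogenous insulin use, the primary marker closest to the trial's objective, is planned as a blood level rather than a recorded dose

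*Combined protocol and SAP*

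**What the plan says.** Under Primary Endpoints, section 5.0 names three markers of pancreatic function: "Blood glucose levels", "HbA1c levels pre-operatively and at the 3 month post-operative visit" and "Exogenous insulin use". A line on measurement follows: "Measured from blood samples 24, 48, 72, 96 hours post op & at 3 months post op". The primary list then adds a decrease in reperfusion injury and "Incidence of diabetes post-operatively". No single endpoint is designated as the main one.

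The sample schedule at the end of section 5.0 has a column headed "Insulin level exogenous", ticked at BS5 to BS9. It also has a C-peptide column, ticked at BS1 and BS5 to BS9. C-peptide is not on the primary list. In the text it appears only as an assay, in a sentence that opens "If the above processing is not part of the costs". For the 3-month visit, the text says "Results of routine lab work performed at the routine 3 month follow-up visit will be collected".

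Section 1.0 sets the objective as preventing reperfusion injury and lowering patients' later need for insulin. Section 7.0 gives general tests for each variable and plans no analysis that combines glucose or HbA1c with insulin.

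**The concern.** Section 2 of the protocol explains that total pancreatectomy leaves patients dependent on insulin. If their insulin is adjusted to their glucose, a poorer graft shows mainly as more insulin given, and less clearly as higher glucose or HbA1c. Insulin use is then the marker in which a nitrite effect would be expected to appear. If it is recorded as a concentration in a blood sample, the trial does not capture the amount given.

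Section 1.0 says that further investigations follow if the data support the hypotheses. A null result on glucose and HbA1c, without a usable insulin measure, could not separate no graft effect from an effect offset by insulin.

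**Working it through.** The plan states no figure on this point, so the check compares the endpoint list with the sample schedule, both in section 5.0.

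| Measurement | Status | Draws ticked | Count |
|---|---|---|---|
| Blood glucose | primary | BS1 to BS9 | 9 |
| HbA1c | primary | BS1, BS9 | 2 |
| Exogenous insulin | primary | BS5 to BS9 | 5 |
| C-peptide | none declared | BS1, BS5 to BS9 | 6 |

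1. *Which marker the measurement line covers.* It names four postoperative times plus 3 months: 4 + 1 = 5. Of the three primary markers, only exogenous insulin is ticked at exactly five draws, and they are the same five times. Glucose has 9 and HbA1c has 2, with its own timing stated. Whether the line belongs to insulin use alone or to all three markers, it covers insulin use.

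2. *Whether a level can stand in for use.* Use is an amount given over a period, for example units/kg/day. A level is a concentration at one moment. It depends on the time since the last dose, on clearance, and on what the graft releases. A patient with a good graft and little injected insulin can have the same level as a patient with a poor graft and much injected insulin. The level therefore need not rank patients by dose or by graft function.

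3. *Whether the other primary endpoints close the gap.* Glucose and HbA1c are weakened as graft markers to the extent that insulin is adjusted to glucose. Incidence of diabetes has no definition, and section 3.1 describes the sample as patients who already have acquired insulin-dependent diabetes. Reperfusion injury is a different construct from insulin need.

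4. *Whether the analysis closes it.* Section 7.0 assigns repeated-measures ANOVA with post-hoc t-tests or chi-square tests. Nothing there reads glucose or HbA1c alongside insulin.

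5. *What is already available.* C-peptide reflects the graft's own insulin. It is ticked six times, once before the study infusion and five times after surgery. Glucose is ticked at all six, so paired values need no extra draw. The cost sentence assumes six draws per patient, which agrees with the six C-peptide ticks, but its condition has no clear consequence. The routine-lab sentence does not mention the research assays that the schedule ticks at BS9.

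**The case against.** A reader might infer that the whole primary set is masked because clinicians hold glucose to target. The documents do not support that. Insulin use and incidence of diabetes are both primary, and insulin use is where an effect would surface under such management. Nor do the documents give a glucose target or a titration rule, so the degree of equalisation is unknown.

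A reader might also conclude that C-peptide should replace glucose and HbA1c as primary. Section 1.0 puts cure rate and insulin need first among the aims, and insulin use matches that directly. In a declared pilot, moving the primary to a mechanistic marker is a preference and not a correction.

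A third inference is that C-peptide will be dropped for cost or not drawn at 3 months. The schedule ticks it without condition, including at BS9, and the measurement line also plans blood samples at 3 months. The cost sentence is too unclear to establish a funding condition. It needs clarifying, no more.

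Finally, the column heading may be loose wording for dose, and the investigators may intend to take doses from the chart. That is possible, but the text says blood samples and describes no dose record. This part of the objection does not remove the problem.

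**Conclusion.** The point holds as a measurement gap in one primary marker. Exogenous insulin use is rightly primary, but at all five of its scheduled times it is specified as a blood level, which does not measure dose. That glucose and HbA1c read alone can miss a graft effect is conditional on insulin being adjusted to glucose, a clinical inference and not a statement in the documents.

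No loss of power can be given. The documents state no effect size, SD or insulin dose for the 10 patients per arm, and any figure would depend on an assumed share of the effect absorbed by insulin. The consequence is one of interpretation: as written, the trial may be unable to say whether similar glucose or HbA1c across arms was reached with similar insulin.

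**What to change.** - Define exogenous insulin use as recorded dose in units/kg/day, taken from medication records, over two stated windows: postoperative days 1 to 4, and a fixed period before the 3-month visit. State which body weight is the divisor; section 7.0 already lists preoperative weight.
- Replace or correct the insulin-level column in the sample schedule, and amend the measurement line so that it no longer covers insulin use.
- State in section 7.0 that glucose and HbA1c will be interpreted together with insulin dose. Both can remain primary.
- Declare 3-month C-peptide, with paired glucose, a key supporting endpoint for graft function, and state the sampling conditions.
- Reconcile the routine-lab sentence and the cost sentence with the BS9 C-peptide tick, so that the draw and the assay are clearly committed.

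The cost is protocol wording, a commitment to an assay already in the schedule, and a small amount of extra data extraction for 30 patients. No additional blood draw is needed.

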1.0 OBJECTIVES

Diabetes is a major health care problem in our country and contributes to the development of severe co-morbidities, including coronary artery disease, heart failure, stroke, renal failure and many others. Whereas the etiology of diabetes is multifactorial, patients with chronic pancreatitis or recurrent acute pancreatitis may acquire insulin-dependent diabetes due to islet cell destruction. Islet cell autotransplantation is the optimal therapeutic approach for many of these patients.

Islet cell autotransplantation is typically done by excision of the pancreas, followed by isolation of the islet cells and then infusion of these cells into the sinusoids of the liver. Isolation of the islet cells occurs in an ischemic and hypoxic environment, resulting in ischemia reperfusion (IR) injury and destruction of islet cells following infusion into the sinusoids. Hence, strategies to prevent IR injury and subsequent islet cell destruction, such as the administration of inhaled nitric oxide (NO) or sodium nitrite (NaNO_2), could enhance islet cell survival following reperfusion, thereby decreasing long-term insulin requirement.

The anion nitrite (NO_2^-) releases NO in biological systems and has been demonstrated to inhibit IR injury (REFS) and improve outcomes (REFS) in patients undergoing Liver transplantation. The objective of this study is to determine whether the NO donor, nitrite will prevent I/R injury and reduce long-term insulin requirements in patients receiving islet cell autotransplantation.

The **central hypothesis** is that in patients undergoing islet cell autotransplantation, infusion of nitrite will inhibit islet cell destruction. The hypotheses of the specific aims are that nitrite will:

- 1) Increase diabetes cure rate - decrease the amount of and/or the need for long-term insulin requirement.
- 2) Decrease the ischemic injury during islet cell procurement,
- 3) Decrease IR injury following islet cell infusion, and

The purpose of this study is to act as a preliminary or “pilot” study. If the data obtained affirm the central hypotheses, further investigations will be conducted to determine mechanism and clinical efficacy.

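### The primary endpoint of exogenous insulin use has blood samples as its only stated source, and these cannot show how much insulin was given or whether it was needed

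*Combined protocol and SAP*

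**What the plan says.** Section 1.0 sets the objective as learning whether nitrite will prevent ischemia-reperfusion injury and "reduce long-term insulin requirements in patients receiving islet cell autotransplantation". The first specific-aim hypothesis is that nitrite will "decrease the amount of and/or the need for long-term insulin requirement". Section 2.3 returns to the amount of long-term insulin in its rationale.

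Section 5.0, Primary Endpoints, names three markers of pancreatic function: blood glucose, HbA1c (before surgery and at 3 months) and "Exogenous insulin use". A fourth bullet at the same level reads "Measured from blood samples 24, 48, 72, 96 hours post op" and adds 3 months. In the table that follows, each row is a blood sample. The insulin column is headed "Insulin level exogenous" and is marked at BS5 to BS9.

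For the 3-month visit, the text describes only the collection of routine laboratory results. Section 6.0 (Experimental Techniques) is marked not applicable, so no insulin assay is described there. Section 7.0 sends all data other than anthropometric and length-of-stay data to a repeated measures ANOVA, with post-hoc t-tests or chi-square tests as appropriate.

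**The concern.** Insulin use is something a patient is given or needs. It is read from a medication record, a prescription or the patient's own account. A blood concentration at one moment shows neither the units given over a day nor whether the patient depends on insulin. Yet blood is the only source the plan attaches to this endpoint, and the table calls it a level.

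Insulin requirement is the outcome in the objective and in hypothesis 1. If staff follow the text as written, the arms will be compared on a concentration, or there will be no value to compare. The other primary markers do not fill the gap. Glucose and HbA1c are themselves affected by the insulin given. Post-operative incidence of diabetes is not defined and could at most speak to need, not amount.

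**Working it through.** The plan gives no figure to reproduce for this point, so the check compares the endpoint list, the table and the named data sources.

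**1. Times.** The measurement line gives 24, 48, 72 and 96 h and 3 months, which is five times. The table marks are:

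- Insulin: BS5 to BS9, five marks, exactly those times.
- Glucose: BS1 to BS9, nine marks. Its post-operative marks are also BS5 to BS9.
- HbA1c: BS1 and BS9, two marks, with its own timing stated in its bullet.

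The line fits the insulin column exactly. It also fits the post-operative part of the glucose column, so the match alone does not prove that the line belongs to insulin only.

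**2. Scope of the line.** If it belongs to insulin use, blood is named as the source. If it is a note for the whole list, insulin use is in the list and blood is still named as the source. The two readings end in the same place.

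**3. Is an assay planned?** The laboratory list covers "running assays for plasma and red cell NOx, C-peptide levels, circulating pro-inflammatory chemokines/cytokines", then immunophenotyping and mRNA, and is costed "assuming 30 patients, each with 6 blood draws". C-peptide, cytokines, immunophenotyping and mRNA are each marked at BS1 and BS5 to BS9: 1 + 5 = 6 samples, which agrees. Insulin has five marks and is not in the list. This leans towards the column being a record of insulin given. It does not settle the matter, because glucose and HbA1c are blood tests and are not in that list either.

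**4. Search for another source.** No surviving section mentions a medication or infusion record, prescription, diary or patient report for insulin. None gives a unit, a collection window or a definition of being off insulin. The list of primary study variables in section 7.0 breaks off after pre-operative BMI, so a lost line cannot be excluded.

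**5. Amount or need.** Hypothesis 1 allows both. Neither can be read from a blood sample, so the conclusion does not depend on which was meant.

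**The case against.** The strongest reply is that the column is a loosely worded dose record. It is qualified as exogenous, insulin is absent from the assay list, and insulin is the only filled column with no mark at BS1. The measurement bullet sits level with the markers and may be no more than a timing note. The table was machine-read, so its header wording is thin evidence. In practice, staff might take doses from the chart anyway.

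Much of this stands. A reader might infer that the sponsor plans an insulin assay and will analyse its result as the endpoint. The documents do not establish that. A reader might also infer a bias, for example because an assay that also reads graft insulin need not move with the dose. No assay is specified, so neither size nor direction can be claimed.

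What the reply does not supply is a source. If the column is a dose record, its label is wrong, the measurement line is wrong for it, and the plan still does not say where the dose comes from, in what unit or over what window.

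Two further points are fair. Section 7.0 does offer a chi-square test, so a yes/no version of insulin use would have a stated comparison. Also, section 1.0 says "If the data obtained affirm the central hypotheses, further investigations will be conducted". A reader might infer that the decision to go on rests on this endpoint. But the hypothesis labelled central concerns islet cell destruction, and insulin requirement belongs to a specific aim. The plural leaves the link open, so it is not relied on here.

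**Conclusion.** The concern holds in this form: the stated measurement rule for a primary endpoint cannot deliver that endpoint, and no surviving text names a source that can. As written, the trial does not capture the long-term insulin requirement in its objective and hypothesis 1.

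The extent is one primary endpoint at all five of its scheduled times. The 3-month value is the most exposed. In-hospital doses should be recoverable from charts, assuming insulin given is charted. At 3 months the plan describes only laboratory results, and this is the time closest to long-term use.

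The conclusion assumes that the cut-off variable list in section 7.0 did not name a dose source. It does not depend on whether use means amount or need, or on whether the measurement line covers one marker or the whole list. It should be fixed, and the repair is small.

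**What to change.** In section 5.0 and its table:

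- Relabel the column as insulin administered, recorded as total daily units and on/off insulin status.
- Name the source. In hospital, use the medication record for the 24 h up to each of the 24, 48, 72 and 96 h points; the four windows then cover the first 96 h without overlap (4 × 24 = 96). At the existing 3-month visit, use the prescription or patient report.
- Limit the measurement line to the blood tests.
- If an insulin assay is also intended, list it separately as a laboratory measure.

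In section 7.0, state that daily units are compared with the planned ANOVA and on/off status with the chi-square test already there.

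The cost for 30 patients is 4 × 30 = 120 chart look-ups and 30 prescription checks or questions at 3 months, with no new sample or visit. The downside is that a patient-reported dose at 3 months is less exact than a hospital record. The change supports comparison between arms. If the sponsor also wants change from before surgery, a pre-operative insulin record would be needed, and the insulin column has no pre-operative entry.

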6.0 EXPERIMENTAL TECHNIQUES

Not applicable

7.0 STATISTICAL CONSIDERATIONS

Primary Study Variables include: Demographics (age, gender, pre-operative weight, pre-operative BMI,

General Data Analysis: All anthropometric data will be compared using unpaired Student's t-test. Length of stay data will be compared using Cox proportional hazard

analysis. All other data will be compared using one-way repeated measures ANOVA with post-hoc analysis by unpaired Student's t-test or Chi Square analysis as appropriated. For all comparisons, a value of $p < 0.05$ will be considered significant.

This is a pilot study. We plan to enroll 10 patients in each of the 3 arms of this study (total N=30).

Study Population Availability: Approximately 8-10 patients present to UAB for this procedure annually. Potential study subjects will be identified by [name] and his clinic team.

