4.2 Randomization Procedure

This is a single institution, blinded, placebo-controlled clinical trial. Patients will be randomized to one of three (3) arms of the study by the research pharmacist:

- Control group (saline infusion will be administered during the pre-isolation and post-isolation phases)

- Pre-isolation infusion (nitrite infusion will be administered during the pre-isolation phase and saline will be administered during the post-isolation phase)
- Post-isolation (saline will be administered during the pre-isolation phase and nitrite infusion will be administered during the reperfusion phase)

Continuous infusion of 32 mg sodium nitrite in 100 mL normal saline at a rate of 10 mL per min over for the duration of the surgery, which are calculated to achieve steady-state plasma concentrations of approximately 10 μ M, concentrations shown to have therapeutic efficacy in animal models of IRI.

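### Section 7.0's one-way repeated-measures ANOVA names no arm or arm-by-time term for a three-arm trial, and its post-hoc tests have no stated contrasts, gate or multiplicity adjustment

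*Combined protocol and SAP*

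**What the plan says.** Section 4.2 sets the design: "Patients will be randomized to one of three (3) arms of the study by the research pharmacist". The arms are saline control, nitrite before islet isolation, and nitrite at reinfusion, with 10 patients each.

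Section 7.0 is the only analysis text. Anthropometric data get an unpaired t-test. For hospital stay, "Length of stay data will be compared using Cox proportional hazard" analysis is named. The rest falls under one sentence: "All other data will be compared using one-way repeated measures ANOVA with post-hoc analysis by unpaired" Student's "t-test or Chi Square analysis as appropriated". The threshold is uniform: "For all comparisons, a value of $p < 0.05$ will be considered significant".

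Section 5.0 supplies the outcomes. The pancreatic-function markers (glucose, HbA1c, exogenous insulin) carry the line "Measured from blood samples 24, 48, 72, 96 hours post op & at 3 months post op". HbA1c is specified as "HbA1c levels pre-operatively and at the 3 month post-operative visit". Post-operative diabetes incidence and reperfusion injury are also listed as primary. Four intraoperative samples (BS1-BS4) are drawn, the first before the study infusion starts, and the sampling table marks glucose at all nine draws.

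**The concern.** A one-way repeated-measures ANOVA ordinarily has one within-patient factor, here time. It asks whether the marker changes over time in the 30 patients pooled. The trial asks whether nitrite patients differ from placebo patients, and whether they diverge over time. Those are the arm and arm-by-time terms, and neither is named.

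On that reading, for these outcomes, nitrite is compared with placebo only by the post-hoc tests. The plan does not say which pairs of arms are tested, at which times, whether a significant ANOVA is needed first, or how the number of tests is handled. Two analysts could run different tests on the same data and both be following section 7.0. Section 1.0 plans further investigation if the data support the central hypotheses, so the result has a use even in a pilot.

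**Working it through.** Section 7.0 gives no power, effect size or SD, so there is no design figure to reproduce beyond 3 × 10 = 30.

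**Inputs from the documents.** Three arms of 10 (4.1, 4.2, 7.0); p < 0.05 per comparison (7.0); five post-operative times (5.0); eight glucose times after BS1 if BS2-BS4 are included (5.0, sampling table).

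**Assumptions not in the documents.** Two-sided tests, complete normal data, compound symmetry, within-patient correlation ρ = 0.3, 0.5, 0.7.

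**1. Does a time-only ANOVA detect nitrite?** Suppose both nitrite arms are shifted by 1 SD at all five times, with no time trend. A constant shift moves a patient's mean but not the within-patient differences between times. The time-only F statistic is therefore unchanged and rejects at its null rate (simulated at ρ = 0.5: 4.7%).

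For a between-arm test on patient means, the variance of a mean is v = ρ + (1 − ρ)/5, or 0.44, 0.60, 0.76. With arm effects 0, 1, 1 the noncentrality is 10 × (2/3)/v = 15.2, 11.1, 8.8. On F(2, 27) the power is 92%, 81%, 71%.

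**2. Error if the t-tests are ungated.** Three arms give three pairs, or two against control. The independence formula 1 − 0.95^k gives 14.3% for k = 3 and 53.7% for k = 15 (five times, three pairs). The tests are correlated, so simulation is needed (20,000 runs, no drug effect; ranges run over ρ = 0.7 to 0.3):

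| Setting | Three pairs | Two pairs v control |
|---|---|---|
| One time (e.g. HbA1c at 3 months) | 12% | 9% |
| Five post-operative times | 34-45% | 27-36% |
| Glucose, BS2-BS9 (eight times) | about 42-60% | 33-49% |

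Under AR(1) correlation the five-time, three-pair figures are 38-46%.

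**3. Does a gate help?** For five times and three pairs:
- Time-ANOVA gate, 1 SD trend shared by all arms: 34-44%, almost no protection.
- Time-ANOVA gate, 0.5 SD shared trend: 23-30% (19-23% under AR(1)).
- Time-ANOVA gate, no trend: about 2%.
- Arm-test gate: about 5%.

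**4. Diabetes incidence.** By exact enumeration at a true incidence of 20-80%, three pairwise chi-squares give at least one false result with probability 8-10%. One three-arm chi-square gives 4-5%.

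**5. Which time to test for insulin.** Suppose the 1 SD effect is present at 3 months only. A three-arm (2-df) test on the average of the five times has effect 1/5 SD and noncentrality (6.67/25)/v, so power is 7-9%. The same test at 3 months alone has noncentrality 6.67 and power about 58%.

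**The case against.** The strongest reply is that the time-only reading is not the only one. The sentence continues a list of between-arm comparisons, unpaired tests fit arms and not times, and 'post-hoc' ordinarily follows an overall test. If arm is the factor and gates the t-tests, error is about 5%. This stands. A reader might infer that the trial will run with a 34-45% false-positive rate, but the documents do not support that: the figure belongs to one reading, and the plan does not say which applies. Even the charitable reading leaves arm-by-time out and the gate unwritten.

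A reader might also take about 42-60% as the error for glucose. That requires testing BS2-BS4, and the primary endpoint list in section 5.0 names only the five post-operative times. On those the figure is the same 34-45%.

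Third, this is a pilot and no decision is tied to a p-value. That justifies exploratory testing and lowers the stakes, but it does not supply the missing arm term, and section 7.0 still labels any p below 0.05 significant.

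Finally, the variable list in section 7.0 breaks off mid-parenthesis, so some text may be lost. Nothing suggests that it named an arm term.

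**Conclusion.** The concern holds in a limited form and should be fixed. What is certain is an omission: the ANOVA stated for a three-arm trial lacks arm and arm-by-time terms, and the post-hoc tests lack contrasts, a gate and an adjustment. What is conditional is the error rate. It is about 5% if arm is the factor and gates the t-tests. It is 34-45% for a five-time marker, and about 12% at one time, if the t-tests are ungated across all three pairs. A time-ANOVA gate with a strong shared trend leaves the five-time figure almost unchanged. All these figures rest on the distribution, correlation and complete-data assumptions listed in the working. The size of any shared trend is also assumed, although some trend is plausible in samples running from surgery to 3 months.

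**What to change.** Before unblinding, replace the sentence in section 7.0 with:

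1. **Exogenous insulin:** a 2-df three-arm test at 3 months, named in advance because the first aim in section 1.0 is long-term insulin requirement. Use a rank-based or permutation version if many values are zero.
2. **Repeated markers:** a mixed model with arm, time and arm-by-time, a covariance structure named in advance, small-sample degrees of freedom, and the BS1 value as covariate where collected. For glucose, model the five post-operative times, take the 2-df arm effect over them as the three-arm test, and report BS2-BS4 descriptively (BS2 precedes islet infusion).
3. **HbA1c at 3 months:** ANCOVA on arm, adjusted for the pre-operative value already collected.
4. **Incidence of diabetes:** one exact or chi-square test across the three arms.
5. **Contrasts:** for each endpoint, compare each nitrite arm with control only if the three-arm test is significant. Report everything else as exploratory estimates with 95% confidence intervals, and state that error is not controlled across endpoints (for five independent endpoints, 1 − 0.95^5 = 23%).

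The cost is one rewritten paragraph, with no new patients, samples or procedures. There will be fewer nominally significant results. The 3-month insulin test also ignores the early values: if a 1 SD effect were present at all five times, its power would be about 58%, against 71-92% for the averaged test.
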